### 4.3. Exclusion Criteria

The presence of any of the following will exclude a subject from enrollment:

- 1. Subject has had prior exposure to anti-CTLA-4, anti-PD-1, anti-PD-L1 mAbs, or cancer vaccines
- 2. Subject has received autologous stem cell transplantation (ASCT) within 12 weeks before the date of randomization.
- 3. History of organ or allogeneic stem cell transplantation
- 4. Subject received any of the following within the last 14 days of initiating study treatment:
  - a. Plasmapheresis
  - b. Major surgery (as defined by the investigator)
  - c. Radiation therapy other than local therapy for myeloma associated bone lesions
  - d. Use of any systemic anti-myeloma drug therapy (except for DARA either alone or in combination with other agents given with it)
- 5. Subject received prior treatment with a monoclonal antibody within 5 half-lives of initiating study treatment, other than DARA.
- 6. Subject is receiving concurrent chemotherapy or biologic or hormonal therapy for cancer treatment. Note: Concurrent use of hormones for noncancer-related conditions (eg, insulin for diabetes and hormone replacement therapy) is acceptable.
- 7. Subject has any of the following laboratory abnormalities:
  - a. Absolute neutrophil count (ANC) < 1,000/µL
  - b. Platelet count:  $< 75,000/\mu L$  (it is not permissible to transfuse a subject to reach this level)
  - c. Hemoglobin < 8 g/dL (< 4.9 mmol/L)(it is not permissible to transfuse a subject to reach this level)
  - d. Creatinine clearance (CrCl) < 45 mL/min (calculated using the Cockcroft-Gault formula or directly calculated from the 24-hour urine collection method)
  - e. Corrected serum calcium > 13.5 mg/dL (> 3.4 mmol/L)
  - f. Serum aspartate aminotransferase (AST) or alanine aminotransferase (ALT) > 2.5 × upper limit of normal (ULN)
  - g. Serum total bilirubin  $> 1.5 \times$  upper limit of normal (ULN) or > 3.0 mg/dL for subjects with documented Gilbert's syndrome
- 8. Subject has clinical evidence of central nervous system (CNS) or pulmonary leukostasis, disseminated intravascular coagulation, or CNS MM
- 9. Subject has known chronic obstructive pulmonary disease (COPD) with a forced expiratory volume in 1 second (FEV1) 50% of predicted normal. *Note that forced expiratory testing (FEV1)is required for subjects suspected of having COPD and subjects must be excluded if FEV1 is* < 50% of predicted normal.

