- 10. Subject has known moderate or severe persistent asthma within the past 2 years (see Appendix F) or uncontrolled asthma of any classification. Note that subjects who

- currently have controlled intermittent asthma or controlled mild persistent asthma are allowed to participate in the study.
- 11. Subject has plasma cell leukemia, Waldenstrom's macroglobulinemia, POEMS syndrome (polyneuropathy, organomegaly, endocrinopathy, monoclonal protein, and skin changes), or amyloidosis
- 12. Subject has nonsecretory MM
- 13. Subject has known allergy or hypersensitivity to study drug formulations
- 14. Subject has active or prior documented autoimmune or inflammatory disorders (including inflammatory bowel disease [eg, colitis, Crohn's disease], diverticulitis, celiac disease, irritable bowel disease, or other serious gastrointestinal chronic conditions associated with diarrhea; systemic lupus erythematosus; Wegener syndrome; myasthenia gravis; Graves' disease; rheumatoid arthritis, hypophysitis, uveitis, etc) within the past 3 years prior to the start of treatment. The following are exceptions to this criterion:
  - a. Subjects with vitiligo or alopecia.
  - b. Subjects with hypothyroidism (eg, following Hashimoto's disease) stable on hormone replacement.
  - c. Psoriasis not requiring systemic treatment.
- 15. Subject has history of primary immunodeficiency
- 16. Subject is positive for human immunodeficiency virus (HIV-1), chronic or active hepatitis B or active hepatitis A or C.
- 17. Subject has received live, attenuated vaccine within 30 days prior to the first dose of DURVA (NOTE: Subjects, if enrolled, should not receive live vaccine during the study and through 30 days after the last dose of DURVA)
- 18. Subject is currently using or has used immunosuppressive medication within 14 days prior to the first study dose of study treatment. The following are exceptions to this criterion:
  - a. Intranasal, topical, inhaled, or local steroid injections (eg, intra-articular injection).
  - b. Systemic corticosteroids at physiologic doses not to exceed 10 mg/day of prednisone or equivalent.
  - c. Steroids as premedication for hypersensitivity reactions (eg, infusion-related reactions, computed tomography [CT] scan premedication).
- 19. Subject has any one of the following:
  - a. Clinically significant abnormal ECG finding at screening
  - b. Congestive heart failure (New York Heart Association Class III or IV)

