# 7.2.1.2.2. Infusion-related Reactions of Grade 3 or Higher

For infusion-related adverse events that are Grade 4, the infusion should be stopped and the subject withdrawn from DARA treatment.

For infusion-related adverse events that are Grade 3, the infusion must be stopped and the subject must be observed carefully until resolution of the adverse event or until the intensity of the event decreases to Grade 1, at which point the infusion may be restarted at the investigator's discretion. Upon restart, the infusion rate should be half of that employed before the interruption.

Subsequently, the infusion rate may be increased at the investigator's discretion. If the intensity of the adverse event returns to Grade 3 after restart of the infusion, then the procedure described in this section should be repeated, or the subject may be withdrawn from treatment. Should the intensity of the adverse event increase to Grade 3 for a third time, then the subject must be withdrawn from DARA treatment.

**Table 6:** Daratumumab Pre Infusion and Post Infusion Medications

Time point	Medication	All Subjects
Pre infusion (~1 hr prior to every daratumumab (DARA)	Oral montelukast (if approved and available)	per investigator discretion prior to first infusion
administration)	Intravenous (IV) corticosteroid	methylprednisolone 100 mg or equivalent dose of an intermediate-acting or long-acting corticosteroid ( Refer to Table 7 for conversion table). Following the second infusion, the dose of corticosteroid may be reduced (methylprednisolone 60 mg intravenously)
	oral antipyretics	acetaminophen 650 to 1000 mg a
	oral or IV antihistamine	diphenhydramine 25 to 50 mg or equivalent
Post infusion Medication (1st and 2nd day after every DARA administration)	oral corticosteroid b	20 mg methylprednisolone or equivalent dose of a corticosteroid in accordance with local standards

<sup>a If necessary, oral preinfusion medications may be administered at the subject's home on the day of the infusion, provided they are given within 3 hours prior to the infusion

**Table 7:** Conversion Table for Glucocorticoid Dose

Generic Name	Oral or Intravenous Dose (mg)
Dexamethasone	0.75
Hydrocortisone	20
Methylprednisolone	4
Prednisolone	5
Prednisone	5

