## 8.2. Prohibited Concomitant Medications and Procedures

The following medications are prohibited (except for the outlined exceptions) during the study. The Sponsor must be notified if a subject receives any of these during the study.

- 1. Subjects who fail ANC, hemoglobin or platelet eligibility criteria at Screening should not be retested for the study after being treated with growth factors or platelet/RBC transfusion.
- 2. Any investigational anticancer therapy.
- 3. Any concurrent chemotherapy, radiotherapy (except palliative radiotherapy), immunotherapy, biologic or hormonal therapy for cancer treatment.
- 4. Immunosuppressive medications including, but not limited to systemic corticosteroids at doses exceeding 10 mg/day of prednisone or equivalent, methotrexate, azathioprine, and tumor necrosis factor alpha (TNF-α) blockers. The following exceptions apply:
  - a. Pre and post infusion medications as outlined in Table 6 and Table 7 for the management of infusion-related reactions.
  - b. Use of immunosuppressive medications in subjects with contrast allergies (eg, CT scan contrast hypersensitivity) is acceptable.
  - c. Use of inhaled, topical, or intranasal corticosteroids or local steroid injections (eg, intra-articular injection) is permitted.

- d. Temporary uses of corticosteroids for concurrent illnesses (eg, food allergies) are acceptable upon discussion and agreement with the Medical Monitor.
- 5. Live attenuated vaccines during the study through 30 days after the last dose of DURVA.
- 6. Herbal and natural remedies are to be avoided.
- 7. Egg cell and sperm donation

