# **8.3.** Required Concomitant Medications and Procedures

- **Infusion reaction prophylaxis:** Pre infusion and post infusion medications for infusion reaction prophylaxis will be given as detailed in Table 6.
- Antiviral prophylaxis: All subjects must initiate antiviral prophylaxis to prevent herpes zoster reactivation within 1 week of starting DARA and continue for 3 months following last dose of DARA.
  - Acceptable antiviral therapy includes acyclovir (eg, 400 mg given orally 3 times a day, or 800 mg given orally 2 times a day or per institutional standards), famciclovir (eg, 125 mg given orally, twice a day or per institutional standards), or valacyclovir (eg, 500 mg given orally, twice a day or per institutional standards), initiated within 1 week after the start of study drug.

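### Exclusion 18c exempts infusion steroids only as premedication, unlike Section 8.2 item 4a; read literally, it can delay Cycle 1 Day 1 for some subjects coming off weekly daratumumab

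*Protocol*

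**What the plan says.** Exclusion 18 (Protocol Section 4.3) looks back 14 days from the first study dose for immunosuppressive medication. Two of its exceptions matter here. Exception 18b allows "Systemic corticosteroids at physiologic doses not to exceed 10 mg/day of prednisone or equivalent". Exception 18c allows "Steroids as premedication for hypersensitivity reactions (eg, infusion-related reactions, computed tomography [CT] scan premedication". Neither mentions steroids given after an infusion.

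The parallel on-study list, Section 8.2 item 4, uses the same 10 mg/day ceiling, but its infusion exception (4a) is wider: "Pre and post infusion medications as outlined in Table 6 and Table 7 for the management of infusion-related reactions". Section 8.3 treats the two halves as one package: "Pre infusion and post infusion medications for infusion reaction prophylaxis will be given as detailed in Table 6". Table 6 sets the doses. Before each DARA infusion the subject receives intravenous "methylprednisolone 100 mg or equivalent dose of an intermediate-acting or long-acting corticosteroid", which may fall to 60 mg methylprednisolone after the second infusion. On each of the next two days the subject takes oral "20 mg methylprednisolone or equivalent dose of a corticosteroid in accordance with local standards".

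Prior DARA needs no washout. Exclusion 4d bars, within 14 days, "Use of any systemic anti-myeloma drug therapy (except for DARA either alone or in combination with other agents given with it". Exclusion 5 applies where "Subject received prior treatment with a monoclonal antibody within 5 half-lives of initiating study treatment, other than DARA". Section 6.1 rules out protocol waivers.

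**The concern.** By Inclusion 2, every subject's last myeloma therapy contained DARA, and Section 1.3.1 rests the hypothesis on adding durvalumab while DARA continues. Exclusions 4d and 5 are written to permit that continuity. Exclusion 18 can undo it. If prior DARA came with a post-infusion steroid above the 18b ceiling, the word premedication leaves that steroid outside 18c, and nothing else in the documents brings it in. The DARA exemption in 4d belongs to criterion 4 and does not carry over to criterion 18.

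The bar has no visible purpose. 18c already exempts the larger pre-infusion dose, and the protocol itself gives the post-infusion steroid on Cycle 1 Day 2, the day of the first durvalumab infusion. At stake is either an avoidable interruption of DARA in progressing disease or a breach of an exclusion criterion. Sites reading 18c by its wording and sites reading it by its purpose would also handle identical patients differently.

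**Working it through.** The protocol states no earliest start date relative to prior DARA, so there is no figure of its own to reproduce.

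**Inputs.** 14-day look-back and 10 mg/day prednisone ceiling (Exclusion 18, 18b). Steroid doses and timing (Table 6). Conversion: methylprednisolone 4 mg = prednisone 5 mg = dexamethasone 0.75 mg (Table 7). Carried-over DARA schedule: weekly (QW), two-weekly (Q2W) or four-weekly (Q4W) (Table 3). *Assumption:* the pre-study post-infusion steroid exceeded the ceiling; the Table 6 dose is used as the example.

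**Step 1, doses in prednisone equivalent.**
- Post-infusion: 20 × 5/4 = 25 mg/day, above 10, so 18b does not cover it.
- Pre-infusion: 100 × 5/4 = 125 mg, or 60 × 5/4 = 75 mg later.
- The ceiling in other units: 10 × 4/5 = 8 mg methylprednisolone; 10 × 0.75/5 = 1.5 mg dexamethasone.
- Per prior infusion, 18c therefore exempts 75-125 mg and leaves 2 × 25 = 50 mg barred.

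**Step 2, earliest Cycle 1 Day 1.** Call the last prior DARA infusion day 0. Earliest start = last steroid day + 14, or + 15 if the fourteenth day counts as inside the window.
- Steroid on days 1 and 2: 2 + 14 = 16, or 2 + 15 = 17.
- Steroid on day 1 only: 1 + 14 = 15, or 1 + 15 = 16.

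**Step 3, delay.** If the subject would otherwise start on day s, the two-day case gives a delay of max(0, 16 − s) to max(0, 17 − s).

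| Otherwise starts on | Delay, two steroid days | Delay, one steroid day |
|---|---|---|
| Day 7 (next QW dose) | 9-10 days | 8-9 days |
| Day 10 | 6-7 days | 5-6 days |
| Day 14 (next Q2W dose) | 2-3 days | 1-2 days |
| Day 17 or later | 0 | 0 |
| Day 28 (next Q4W dose) | 0 | 0 |

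The next scheduled dose is the earliest natural start, not a required date.

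**Step 4, size against the protocol's own tolerances.** Section 6.2 allows ±3 days on all visits. Section 7.2.4.2 (Table 8) calls a QW dose missed when it is more than 3 days late and a Q2W dose missed when more than 7 days late. The Q2W delay of 2-3 days sits inside both. The QW delay skips the day-7 dose and makes the day-14 dose 2-3 days late.

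**Step 5, steroid the protocol gives in study Days 1-14.** QW, infusions on Days 1 and 8: 2 × 125 + 4 × 25 = 350 mg prednisone equivalent over 6 days. Q2W or Q4W, infusion on Day 1: 125 + 2 × 25 = 175 mg over 3 days. This shows inconsistency with the entry rule, not harm.

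**The case against.** The strongest reply is that the effect hangs on a fact the documents do not contain. Table 6 governs on-study dosing and even there defers to local standards; nothing says what steroid followed pre-study DARA. That stands, and the finding is conditional for that reason.

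Second, a day-7 start is a best case. Screening requires consent, marrow aspirate and biopsy, central laboratory work, 24-hour urine and sponsor eligibility review (Sections 6.1, 6.4 and 7.3), and may take up to 28 days. If DARA is not redosed meanwhile, screening may absorb the whole wait. This stands too: the full 9-10 days needs either a very fast start or weekly DARA continued through screening, and the documents establish neither as typical.

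Third, 18c names infusion-related reactions, Section 8.3 describes pre- and post-infusion drugs together as prophylaxis, and Section 6 sends protocol questions to the Medical Monitor. Clarifying an ambiguous word is not a waiver. A reading by purpose is therefore available and would remove the problem. But the text of 18c does not say it, and Section 8.2 item 4a shows that the authors wrote post-infusion explicitly when they meant it.

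Fourth, no clinical effect of a 9-10 day gap is shown. These subjects have already progressed on DARA, and the protocol tolerates toxicity delays of up to 28 days before DARA is stopped for good. This limits severity; it does not supply a reason for the bar.

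**Conclusion.** The mismatch between 18c and Section 8.2 item 4a is in the text, and the date arithmetic holds on its stated assumption. The material consequence is confined to QW subjects who had a post-infusion steroid above 8 mg/day methylprednisolone and who either continue weekly DARA into screening or could start quickly. For them the literal rule means up to 9-10 days' avoidable gap, or a deviation that cannot be waived. At or below 8 mg/day, with no post-infusion steroid, or where the start would fall on or after day 17 anyway, 18c causes no delay.

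A reader might infer that criterion 18 shuts out patients whose disease progressed on DARA, or that the whole population starts 9-10 days late. The documents support neither. The bar lapses by day 17 at the latest under the Table 6 pattern, the wait is shorter than the 28-day screening window, and the pre-study steroid use that would trigger it is not reported. Nor does the point reach the inference: the full analysis set (all enrolled subjects), the 18 + 32 subject design and its power are unchanged. Severity is low.

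**What to change.** At the next amendment, reword 18c to match Section 8.2 item 4a, for example: *Steroids as pre- or post-infusion prophylaxis for hypersensitivity or infusion-related reactions (including those given with DARA), or as CT scan premedication.* The cost is one phrase, with no added visits, procedures or patients. Exclusion 18 would then impose no wait because of DARA infusion prophylaxis.

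The change does not help subjects whose prior DARA regimen included therapeutic dexamethasone above 1.5 mg/day. Exclusion 4d lets agents given with DARA continue, and Section 1.2.2 describes DARA regimens containing dexamethasone, yet Exclusion 18 would still bar it within 14 days. Whether that is intended is a separate question for the sponsor; asking it is not itself a remedy.

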# 5. TABLE OF EVENTS

**Table 4:** Table of Events

	Screening Period					,	Freatment Perio	od		0/1/1	Follov	v-up Period
Events		C 1-2 (±3 days)			C 3-6 (±3 day		≥ C7 (±3 days)	(±3		90 days (+3) after last		
	-28 to -1	D1 a	D 2	D8	D 15	D 22	D 1	D 15	D1	discon decision)	(+3) after EOT	DURVA/ DARA dose
Informed consent	X	-	-	-	-	-	-	-	-	-	-	-
Inclusion/exclusion criteria	X	-	-	-	-	-	- 0		-	-	-	-
IRT registration	X	X	-	-	-	-		-	-	X	-	-
Complete medical history	X	-	-	-	-	-	X -Y	-	-	-	-	-
Demographics	X	-	-	-	-		_	-	-	-	-	-
Prior disease history	X	-	-	-	-	0-/	-	-	-	-	-	-
Prior disease therapies	X	-	-	-		(-)	-	-	-	-	-	-
Forced expiratory volume test, (subjects with COPD)	X	-	-	-	X	-	-	-	-	-	-	-
Prior/concomitant medication evaluation	X (-28 days from the date when ICF was signed)		Q	Cont	inuous	until 90	days after last	dose of I	DURVA or	DARA, whichev	ver is later	
Blood Type, Rh, and IAT	-	X	-	-	-	-	-	-	-	-	-	-
Prior/concomitant procedures evaluation	X (-28 days from the date when ICF was signed)			Cont	inuous	until 90	days after last	dose of I	OURVA or	DARA, whichev	ver is later	
AE evaluation	Continuous st	arting	after in	forme	d conse	ent signa	ture, until 90 da	ays after	last dose of	DURVA or DA	RA, whic	hever is later
Physical examination	X	X	-	-	-	-	X	-	X	X	-	-

**Table 4:** Table of Events (Continued)

	Screening Period	Treatment Period						Follow-up Period				
Events			C 1-2 (±3 days)		C 3-6 (±3 days) ≥ C7 (±3 days)		EOT (≤7 days from trt	28 days (+3)	90 days (+3) after last			
	-28 to -1	D1a	D 2	D8	D 15	D 22	D 1	D 15	D.1	discon decision)	after EOT	DURVA/ DARA dose
Vital signs	X	X	X	X	X	X	X	X	X	X	X	X
Height	X	-	-	-	-	-	-	-		-	-	-
Weight	X	X	X	X	X	X	X	X	X	X	X	X
12-lead ECG	X	C1	-	-	-	1	C6	1	-	X	-	-
Hepatitis and HIV-1 antibody testing	X	-	-	-	-	-		-	-	-	-	-
Hematology	X	X	X	X	X	X	X	X	X	X	X	X
Coagulation parameters	X	X	-	-	X		X	-	X	X	-	-
Chemistry	X	X	X	X	X	X	X	X	X	X	X	X
Thyroid Function Tests (TSH and free T3/T4 at Screening and Cycles 1-4; TSH for Cycle 5 onwards; reflex testing for free T3/T4 only if TSH is abnormal)	X	X	-	-	9	-	X	-	X	X	-	X
Renal Function (CrCl)	X	X	X	X	X	X	X	X	X	X	X	X
Urinalysis	X		X		if	clinicall	y indicated			X	X	X
Pregnancy Testing (FCBP only) Refer to Section 6.1	X	X	P		-		X	-	X	Х	X	X

**Table 4:** Table of Events (Continued)

	Screening Period					,	Treatment Peri	od			Follov	v-up Period
Events			C 1-2 $C$ 3-6 $C$ 3-7 $C$ 3-7 $C$ 3-7 $C$ 3-7 $C$ 3-8				$ \begin{array}{c cccc} C & 1-2 & C & 3-6 & (\pm 3) \\ (\pm 3) & days & (\pm 3) & days & days \end{array} $ EOT		EOT (≤7 days from trt	28 days (+3)	90 days (+3) after last	
	-28 to -1	D1a	D 2	D8	D 15	D 22	D 1	D 15	D.1	discon decision)	after EOT	DURVA/ DARA dose
Antiviral prophylaxis	-		Initiate	withi	n 1 wee	ek of star	ting DARA an	d continu	e for 3 mor	nths following las	st dose of	DARA.
EFFICACY AND OTHER ASS	SESSMENTS								1			
ECOG Performance status	X	X	-	-	-	-	X	1-	X	X	-	-
Assessment of response (IMWG Uniform Response Criteria) b	-	C2	-	-	-	-	X		X	X	-	-
Serum and urine protein electrophoresis	X	X	-	-	-	-	X	-	X	X	-	-
Serum and urine immunofixation	X	X	-	-	-		X	-	X	X	-	-
Serum free light chains assay	X	X	-	-	0	-	X	-	X	X	-	-
Quantitative serum immunoglobulin	X	X	-		)-(	-	X	-	X	X	-	-
EMP clinical assessment	X	X	-<	7	-	-	X	-	X	X	-	-
EMP radiological assessment (only required if history of or clinical indication of EMPs only assessable radiographically)	X	<	Day I starting at C3, then every 3 cycles thereafter X							-		
Skeletal Survey for bone lesions	X (within 60 days prior to first dose is acceptable)	I	Repeated during treatment if clinically indicated to confirm response or PD						onse or PD		-	

**Table 4:** Table of Events (Continued)

	Screening Period					ŗ	Freatment Peri	od			Follov	v-up Period
Events				C 1-: (±3 da			C 3-6		≥ C7 (±3 days)	EOT (≤7 days from trt	28 days (+3)	
	-28 to -1	D1a	D 2	D8	D 15	D 22	D 1	D 15	D.1	discon decision)	after EOT	DURVA/ DARA dose
Bone marrow aspirate and/or biopsy sampling for cytogenetics, % plasma cells,	X BMA and BMB cytogenetics, % plasma cells,	- BM	(A and	ВМВ	at time	of CR c	onfirmation for	r % plasm	na cells	− GCI		
β2-microglobulin	X	X	-	-	-	-	X	-	X	X	-	-
Pre- and post-DARA infusion medications c (Refer to Section 7.2.1.2)	-	X	-	X	X	X	X	X	X	-	-	-
DARA IV administration (QW, Q2W, or Q4W) Refer to Section 7.2.2	-	X d	-	X d	Xd	X d	X d	X d	X d	-	-	-
DURVA IV administration	-		D2 D1 e		)`	-	Xe	-	Xe	-	-	-
Study treatment (DURVA, DARA) accountability/compliance	-	X	X	X	X	X	X	X	X	X	-	-
Blood sample for DURVA PK (Refer to Section 6.5.1)		C2	C1	C1	C1	C1	C4,C6	-	C10, C14	-	-	-
Blood sample for DARA PK (Refer to Section 6.5.2)		C1	-	C1	C1	C1	-	-	-	X	X	X

**Table 4:** Table of Events (Continued)

	Screening Period					ŗ	Γreatment Peri	od			Follov	v-up Period
Events			C 1-2 (±3 days)			C 3-6 (±3 days)		≥ C7 (±3 days)	EOT (≤7 days from trt	28 days (+3)	90 days (+3) after last	
	-28 to -1	D1a	D 2	D8	D 15	D 22	D 1	D 15	D1	discon decision)	after EOT	DURVA/ DARA dose
CCI									7			
_												-

AE = adverse event; BMA = bone marrow aspirate; BMB = bone marrow biopsy; C = Cycle; COPD = chronic obstructive pulmonary disease; CR = complete response; CrCl = creatinine clearance; D= Day; DARA = daratumumab; DURVA= durvalumab; ECG = electrocardiogram; ECOG = Eastern Cooperative Oncology Group; eCRF= electronic case report form; EMP = extramedullary plasmacytomas; EOT = End of Treatment; FCBP = female of childbearing potential; HIV = human immunodeficiency virus; IAT = indirect antiglobulin test; IMWG = International Myeloma Working Group; IRT= Interactive Response Technology; IV = intravenous; PD = disease progression; PK = pharmacokinetics; QW = weekly; Q2W = every 2 weeks; Q4W = every 4 weeks; TSH= thyroid stimulating hormone; trt discon = treatment discontinuation.

- a On Cycle 1 Day 1 (C1D1), safety laboratory assessments must be performed locally (central confirmation is not required) to confirm subject continues to meet the required safety laboratory values prior to initiating study treatment. However, if screening assessments were performed within 72 hours of C1D1, safety laboratory and physical examinations need not be repeated at C1D1.
- b Per IMWG Uniform Response Criteria all response categories and progressive disease require 2 consecutive assessments.
- c Pre infusion medications to be given before all daratumumab infusions (if necessary, oral pre infusion medications may be administered at the subject's home on the day of the infusion, provided they are given within 3 hours prior to the infusion); post infusion medications to be given on the first and second days following all daratumumab infusions.
- d Every effort should be made to keep subjects on the planned dosing schedule (QW, Q2W, or Q4W) as detailed in Section 7.2.2. However, doses given within 3 days of the scheduled dose are permitted, as long as the interval between doses is at least 5 days. Blood pressure is to be measured at the following time points on C1D1 and C1D8: immediately before the start of the infusion; at approximately 30 minutes, 1 hour, 90 minutes, 2 hours, and 3 hours 30 minutes after the start of the infusion; at the end of the infusion; and 30 minutes and 1 hour (+/- 5 minutes) after the end of the infusion. For all other DARA infusions, blood pressure will be measured immediately before the infusion start and at the end of the infusion.
- e **First DURVA infusion:** blood pressure and pulse will be monitored, as follows (based on a 60-minute infusion): Prior to the beginning of the infusion (measured once from approximately 30 minutes before up to 0 minutes [ie, the beginning of the infusion]); approximately 30 minutes during the infusion (halfway through infusion); at the end of the infusion (approximately 60 minutes ±5 minutes). If the infusion takes longer than 60 minutes, then blood pressure and pulse measurements should follow the principles as described above or be taken more frequently if clinically indicated. For DURVA infusions on C2D1 onward, a +24 hour window is allowed and may be implemented per

investigator discretion.

Subsequent DURVA infusions: vital signs will be measured prior to the start of the infusion. Subjects should be carefully monitored and blood pressure and other vital signs should be measured during and post infusion as per institution standard and as clinically indicated. Any clinically significant changes in vital signs should be entered onto an unscheduled vital signs eCRF page.

